5.2.2. Accuracy

The accuracy will be assessed using the Brier score:

$$\text{Brier Score} = \frac{1}{N} \sum_{i=1}^n (Y - p)^2$$

Where Y is the observed outcome and p is the prediction of the model

The Brier score depends on the prevalence of the outcome, the investigators will also calculate the scaled Brier score to account for the baseline risk of Massive transfusion:

$$\text{Scaled Brier score} = \frac{1 - \text{Brier}}{\text{Brier max}}$$

The scaled Brier score ranges from 0% to 100% and indicates the degree of error in prediction. A scaled Brier score of 0% shows perfect accuracy.

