2.1 Background and rationale

Since the 2000s, many prognostic scores were developed to predict traumatic haemorrhage. Most of these studies were retrospectives based on registers. Due to missing data on death due to bleeding, these studies chose to predict the massive transfusion risk as a surrogate of haemorrhagic death. These scores include clinical parameters (vital signs), laboratory values (Haemoglobin, lactate, Base excess) and/or imaging (CT or ultrasound) values. The scores showing best performance are the Trauma Associated Severe Haemorrhage (TASH) score, developed and validated on the German register (DGU-Register) (1, 2) and the ABC score developed and validated in the United States of America (3, 4). The scores with variables are described on Figure 1,2.

However, the majority of these scores cannot be applied at the trauma scene due to the unavailability of laboratory and imaging values. Therefore, their clinical utility remains unclear. To overcome the need for diagnostic tests, authors have developed and recently validated a clinical prognostic score in identifying trauma patients with, or at risk of, significant haemorrhage based on predicted probabilities of death due to bleeding: BATT score (5). This score was developed from an international cohort using data from 271 Trauma Centres in 41 countries on 5 continents and uses first clinical parameters at initial assessment. The BATT score predicts death due to bleeding and has been validated on a large population in England and Wales. It could also predict massive transfusion, as a surrogate of haemorrhagic death, earlier at the trauma scene. Its feasibility and external validation would make its clinical utility superior to other scores while identifying a greater number of patients requiring early management.

Our study is an external validation of pre-existing prognostic scores of traumatic haemorrhages (TASH^{1,2}, ABC^{3,4} and BATT⁵ score) at different times of care (Scene of Injury, admission at the trauma room) in order to assess their overall performance, discrimination and calibration in the prediction of massive transfusion, and haemorrhagic death. The objective of the study is to assess a comparison of score performances (Overall performance, discrimination and calibration).

3. Study Methods

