6.2.2 Secondary outcome

Secondary outcomes are death due to bleeding if available in the registry, early death (< 24 hours) and coagulopathy at hospital admission defined by an INR > 1.2 or TP $< 70\%$ or Fibrinogen ≤ 1.5 g/L (each other will be used for sensibility analysis)^{7,8,9}.

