5.2. Analysis methods

5.2.1. Efficacy analyses of primary outcome

First, the investigators will assess the accuracy (overall performance), discrimination and calibration of ABC, TASH and BATT score for the prediction of massive transfusion in trauma patients at the trauma scene and at the hospital admission.

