5.2.4. Calibration

Calibration is the agreement between observed and predicted outcomes. The investigators will mostly estimate calibration as the difference between the mean predicted and observed probabilities and the ratio of the predicted and observed number of events (P/O). The investigators will plot the observed and predicted probabilities of massive transfusion by decile of the score and with local regression based on LOESS algorithm. The investigators will estimate the calibration intercept and slope of the calibration plot as a measure of spread between predicted and observed outcome. Ideally, the intercept would be zero indicating that the predictions are neither systematically too low or too high and the slope would be 1.

Unfortunately, the investigators cannot estimate the calibration of the BATT score, because of its different outcome (death due to bleeding and not the massive transfusion as the TASH and ABC score). For the BATT, calibration will be assessed with the outcome of death due to bleeding or early death.

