5.2.1.1 Efficacy analyses of secondary outcome

The investigators will perform the same analysis for secondary outcomes as the primary outcome.

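### The Brier score for massive transfusion is planned for BATT although the SAP withdraws BATT's calibration for that outcome, and the same mismatch recurs for the secondary outcomes

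*SAP*

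**What the plan says.** SAP 5.2.1 (primary outcome) plans to "assess the accuracy (overall performance), discrimination and calibration of ABC, TASH and BATT score for the prediction of massive transfusion". SAP 5.2.2 (Accuracy) measures overall performance by the Brier score, "Where Y is the observed outcome and p is the prediction of the model", and adds that "the investigators will also calculate the scaled Brier score to account for the baseline risk of Massive transfusion". Neither section excludes a score. The protocol synopsis (Statistical Considerations) also lists the Brier score as the overall-performance measure for comparing the scores, again without exception.

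SAP 5.2.4 then states: "Unfortunately, the investigators cannot estimate the calibration of the BATT score, because of its different outcome". It moves BATT's calibration, and only its calibration, to death due to bleeding or early death. For the other scores it will "plot the observed and predicted probabilities of massive transfusion by decile of the score".

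SAP 5.2.1.1 says: "The investigators will perform the same analysis for secondary outcomes as the primary outcome". The outcomes concerned are listed in the SAP's outcome definitions: "Secondary outcomes are death due to bleeding if available in the registry, early death (< 24 hours) and coagulopathy at hospital admission".

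SAP Figure 1 tabulates an MT probability for TASH. Figure 2 gives ABC as 0 to 4 points with a cut-off of 2 or more and no probability. There is no figure for BATT.

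**The concern.** A Brier score compares a predicted probability with the observed outcome, so it rewards calibration as well as discrimination. If a probability of death due to bleeding is inserted where Y is MT, part of the score measures only how far the two outcomes differ in frequency. That is the reason 5.2.4 gives for not calibrating BATT against MT, and it applies equally to 5.2.2.

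SAP 2.1 makes the comparison of overall performance, discrimination and calibration the study's objective, so the Brier comparison is a main result. As planned, a score that ranks patients less well than BATT could be reported as more accurate. For the secondary outcomes the mismatch falls on TASH and ABC against death, and on all three scores against coagulopathy. BATT against death due to bleeding is a matched pair and is not in question.

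ABC has a further gap. Its Brier score, predicted-to-observed ratio (P/O), intercept and slope all need a probability that the SAP does not name.

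**Working it through.** **No planned figure to reproduce.** The documents state no Brier value and no event rate. All rates below are assumptions.

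**Step 1: the algebra.** Let r be the true risk of the observed outcome given the score, and p the probability used. Then

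Brier = E[r(1 − r)] + E[(r − p)²].

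The second term is calibration error. It is zero only if p is calibrated for the outcome being scored. This needs no assumed rate.

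**Step 2: the model.** Take r = expit(a + 1.25z) with z standard normal, and solve a for the assumed rate of the observed outcome. This gives AUROC 0.804, 0.800 and 0.794 at rates of 3%, 5% and 10%. Take p = expit(a′ + 1.25z), with a′ solved for the rate of the outcome that p was built for. Ranking is then identical, and p is perfectly calibrated for its own outcome. Values come from numerical integration, so there is no simulation error. The scaled score is the conventional 1 − Brier/[π(1 − π)], where π is the rate of the observed outcome.

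**Step 3: BATT-type mismatch against MT.** For MT 5%, π(1 − π) = 0.0475 and the matched Brier is 0.04305, so the matched scaled score is 1 − 0.04305/0.0475 = 9.4%. With p for a 2% outcome, the added calibration error is 0.0022, giving 1 − (0.04305 + 0.0022)/0.0475 = 4.7%.

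| MT rate | Rate p was built for | Scaled Brier, matched | Scaled Brier, mismatched |
|---|---|---|---|
| 5% | 4% | 9.4% | 8.9% |
| 5% | 3% | 9.4% | 7.4% |
| 5% | 2% | 9.4% | 4.7% |
| 5% | 8% | 9.4% | 5.6% |
| 3% | 2% | 6.7% | 5.8% |
| 10% | 5% | 13.9% | 8.6% |
| 10% | 2% | 13.9% | −0.8% |

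At 5% against 2%, changing the slope to 1.0 or 1.6 (AUROC 0.75 or 0.85) gives 5.8% to 2.1%, or 15.3% to 9.3%.

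**Step 4: the loss as discrimination.** Find the AUROC at which a well-calibrated MT score has the same scaled Brier as the mismatched one. At MT 5% with p for a 4%, 3% or 2% outcome, it is 0.795, 0.777 or 0.736, against a true value of 0.800. At MT 3% with p for a 2% outcome it is 0.790, against 0.804.

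**Step 5: secondary outcomes, with p built for MT at 5% (TASH).** P/O is the rate of the predicted outcome divided by the rate of the observed one.

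| Observed outcome | Matched | With the MT probability | P/O |
|---|---|---|---|
| Coagulopathy 10% | 13.9% | 8.6% | 5/10 = 0.50 |
| Coagulopathy 20% | 19.0% | −3.3% | 5/20 = 0.25 |
| Coagulopathy 30% | 21.7% | −20.0% | 5/30 = 0.17 |
| Death 3% | 6.7% | 3.5% | 5/3 = 1.67 |

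With weaker discrimination for coagulopathy at 20% (true-risk slope 0.8, AUROC 0.70), the fall is from 9.2% to −7.5%.

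**Step 6: which probabilities the SAP supplies.** For 9 to 23 points, the TASH table fits logit(p) = −5.456 + 0.303 × TASH to within about 0.5 percentage points. It gives only bounds for 1 to 8 and for 24 or more points, and nothing for 0. ABC has no printed probability, and its five possible values form at most five groups, not deciles. BATT's probability is not printed either, although SAP 2.1 describes that score as resting on predicted probabilities of death due to bleeding.

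**The case against.** - **The source of p is open.** The wording of 5.2.2 could cover a logistic model refitted in the registry for each score, and then no penalty arises. But a refitted p would also make BATT's MT calibration estimable, which 5.2.4 says it is not. The refit reading therefore conflicts with the SAP's own text.
- **5.2.1.1 may carry the 5.2.4 rule over.** On that reading, TASH would not be calibrated against coagulopathy. Even so, 5.2.4 states its exception for BATT and for calibration only. It would not cover the Brier score, and the text does not extend it to TASH or ABC.
- **The size is assumed and may be small.** This stands. At 5% against 4% the loss is 0.5 points, about 0.0002 on the raw Brier scale; at 5% against 2% it is 0.0022 on a matched Brier of about 0.043. The documents do not say which outcome is rarer, but the penalty also arises when p is for a commoner outcome (5% against 8%: 9.4% to 5.6%). Real scores may also be miscalibrated for their own outcomes, so which score the comparison would favour is unknown.
- **Deciles for ABC are a matter of presentation.** This also stands; no estimate changes.
- **Recalibrating in the same registry is no longer validation of the original scores.** Correct, and the reason such results must be labelled.

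**Conclusion.** The concern holds. The conflict between 5.2.2 and 5.2.4 is in the text, and Step 1 shows it matters whatever the event rates, unless p happens to be calibrated for the outcome scored. Followed as written, the plan gives a distorted comparison of overall performance.

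The size depends on assumed rates, a logistic risk model and perfect calibration of each score for its own outcome. Within those assumptions it ranges from negligible when the rates are close to large enough to turn a useful score's scaled Brier negative (MT 10% against 2%; coagulopathy at 20% or 30%). AUROC, sensitivity, specificity and likelihood ratios are unaffected, so the planned comparison of discrimination on MT stands. The plan should be corrected before analysis; the point does not undermine the study as a whole.

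**What to change.** 1. Extend the BATT exception in 5.2.4 to 5.2.2 (Accuracy), and state in 5.2.1.1 which score-outcome pairs are analysed. Limit Brier and calibration on original probabilities to matched pairs: TASH for MT, and BATT for death due to bleeding or the proxy defined in the SAP's missing-data section. Label early death (under 24 hours) as a surrogate.
2. For any three-score Brier comparison, or any mismatched outcome, first recalibrate each score to that outcome in the registry by logistic regression and label the result as recalibrated. Treat ABC this way too, unless a published ABC probability is named in advance. Do not report calibration intercept and slope for a score recalibrated in the same data: they are 0 and 1 by construction.
3. Show ABC by its five values, with observed risk and 95% CI, instead of deciles.
4. As smaller additions, name the source of BATT's probability, and state the numeric p used for TASH 0, 1 to 8 and 24 or more points.

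The cost is SAP wording and modest extra code, with no new data. The real downside is that the three-score Brier comparison then describes recalibrated scores, not the scores as published. Discrimination remains the direct comparison of all three on MT.

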
Study Duration:
	
11 months

Study Schedule:
	
From August 2020 to June 2021

Investigator(s):	
[name] Study Director Service des Urgences Centre hospitalier Universitaire Vaudois (CHUV) [name] [name] Email : [contact]
 
Doctor [name] Study Director Service des Urgences Centre hospitalier Universitaire Vaudois (CHUV) [name] [name] Email : [contact]
 
[name] Principal investigator Service des Urgences Centre hospitalier Universitaire Vaudois (CHUV) [name] [name] Email : [contact]

Study Centre(s):	
Multi-centre study including 12 Swiss Trauma Centre included in the Swiss Trauma Registry (Centre Hospitalier Universitaire Vaudois, Hôpitaux universitaire Genevois, Inselspital Bern, Universitätsspital Basel, Universitätsspital Zürich, Kantonsspital St. Gallen, Luzerner Kantonsspital, Kantonsspital Aarau, Kantonsspital Graubünden, Kantonsspital Winterthur, EOC – Ospedale Regionale di Lugano, Gesundheitsnetzwerk Wallis – Standort Sion)

Statistical Considerations:	
Comparison between scores:
 
 - Overall performance: Brier score - Discrimination: C-statistic, AUROC curve and calculation of likelihood ratio, sensitivity and specificity. - Calibration: Global calibration, calibration curve with intercept and slope calibration. 
Missing data: To estimate baseline risk for the full dataset, we will replace missing predictors using multiple imputation by chained equation.
 
Please referring to the Statistical Analysis Plan

GCP Statement:	
This study will be conducted in compliance with the protocol, the current version of the Declaration of Helsinki, the ICH-GCP or ISO EN 14155 (as far as applicable) as well as all national legal and regulatory requirements.

Study Procedure/Flowchart with Timelines: Study specific Examinations have to be clearly identified

1st step :Request database to the Swiss trauma registry, redacting the statistical analysis plan and study registration on Clinicaltrials.org (August-September 2020)

2nd step: Statistical Analysis (October 2020)

3rd step: Results (December 2020)

4th step: Publication

Storage of Data-and Samples for Future Research Aims: no**Ethical Considerations:**

1. Please describe the potential gain of new knowledge obtained with this study, and its meaning for patients/society.

Answer n°1:

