5.3 Subgroup analyses

If the sample size permits, the investigators will conduct subgroup analysis in different subpopulations for the primary and secondary outcomes. The investigators will create the following subgroups in our MTP study:

- Subgroup 1: subdivide the population into two groups: with or without isolated severe traumatic brain Injury (TBI) with AIS HEAD ≥ 3 and AIS thorax/abdominal <3 and/or AIS lower extremity < 4 .
- Subgroup 2: subdivide the population into two groups: with or without anticoagulation treatment before trauma.

- Subgroup 3: subdivide the population into two groups: with or without trauma-induced coagulopathy.
- Subgroup 4: subdivide the dataset in prehospital settings and in-hospital settings.
- Subgroup 5: All analysis and results will be present into two subgroups: missing data imputed and missing data excluded with the complete case analysis.
- Subgroup 6: The investigators will test the heterogeneity of the performance parameters of each centre and the investigators will potentially exclude data from centre with homogeneous case mixes.
- Subgroup 7: subdivide the population into two groups: low-volume prehospital fluid replacement (<1500 ml) and High-volume prehospital fluid replacement (>1500ml).

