----------------------------------------------------------------------------------------------------------------------------------------------------------------------------------------------------------------------------------------------------------------------------------------------------------------------------------------------------------------------------------------------------------------------------------------------------------------------------------------------------------------------------------------------------------------------------------------------------------------------------------------------------------------------------------------------------------------------------------------------------------------------------------------------------------------------------------------	-------------------------------------------------------------------------------------------------------------------------------------------------------------------------------------------------------------------------------------------------------------------------------------------------------------------------------------------------------------------------------------------------------------------------------------------------------------------------------------------------------------------------------------------------------------------------------------------------------------------------------------------------------------------------------------------------------	-----------------------------------------------------------------------------------------------------------------------------------------------------------------------------------------------------------------------------------------------------------------------------------------------------------------------------------------------------------------------------------------------------------------------------------------------------------------------------------------------------------------

Figure 1. TASH score²

Variable	Value	Points	Score
Haemoglobin (g/dl)	< 7	8	
	< 9	6	
	< 10	4	
	< 11	3	
	< 12	2	
Base excess (mm)	< -10	4	
	< -6	3	
	< -2	1	
Systolic blood pressure (mmHg)	< 100	4	
	< 120	1	
Heart rate (bpm)	> 120	2	
Free intraabdominal fluid (e.g. by FAST)		3	
Clinically instable pelvic fracture		6	
Open or dislocated femur fracture		3	
Male gender		1	
TASH > (sum of score points)			

Probability for massive transfusion (MT)	
TASH	P
1-8	< 5%
9	6%
10	8%
11	11%
12	14%
13	18%
14	23%
15	29%

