16	35%
17	43%
18	50%
19	57%
20	65%
21	71%
22	77%
23	82%
24 +	>85%

Figure 2. ABC score³

Variable	Value	Points
Penetrating mechanism	Positive	+ 1
	Negative	0
Systolic Blood Pressure	≤ 90 mmHg	+ 1
	< 90 mmHg	0
Heart Rate	≥120 bpm	+ 1
	<120 bpm	0
FAST	Positive	+1
	Negative	0
ABC score positive for high risk of massive transfusion if ≥ 2 points		

References

- 5) Ageron F-X, Gayet- Ageron A, Steyerberg E, et al. Prognostic model for traumatic death due to bleeding: cross-sectional international study. *BMJ Open* 2019; e026823. doi:10.1136/ bmjopen-2018-026823
- 6) Swiss trauma Board, <http://www.swisstraumaboard.ch>

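### SAP 5.2.2 defines the scaled Brier score by a formula that contradicts its stated direction and range, and leaves Brier max undefined

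*SAP*

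**What the plan says.** SAP section 5.2.2 defines the Brier score as the mean squared difference between the observed outcome and the prediction, so 0 is perfect. It notes that this depends on prevalence and adds that "the investigators will also calculate the scaled Brier score to account for the baseline risk of Massive transfusion". The formula printed for the scaled score is a single fraction, with 1 − Brier above the line and Brier max below it. Two statements on interpretation follow: "The scaled Brier score ranges from 0% to 100% and indicates the degree of error in prediction", and "A scaled Brier score of 0% shows perfect accuracy".

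Neither document defines Brier max. The Protocol synopsis (Statistical Considerations) names only the unscaled measure, "Overall performance: Brier score", and refers to the SAP for the rest.

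The measure is meant for use beyond one comparison. SAP section 5.2.1.1 repeats the analysis for the secondary outcomes. Section 5.3 lists subgroups and adds that "The investigators will test the heterogeneity of the performance parameters of each centre".

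**The concern.** The formula, the range and the direction cannot all be right. A reader who follows the prose would call a score accurate when its scaled value is low, whereas the printed formula gives low values to inaccurate scores.

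The scaled score is the SAP's stated means of accounting for baseline risk, so it matters most where event rates differ: between centres, between subgroups and between outcomes. There the unscaled Brier score is not a reliable check, because it moves with prevalence. SAP section 3.3 says the plan is to be posted before the dataset arrives. With the formula, direction and denominator unsettled, the choice among them would in effect be made after the data are seen.

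The risk applies to any score that yields predicted probabilities. It does not amount to a wrong three-score ranking on massive transfusion. SAP Figure 1 tabulates probabilities for TASH ("Probability for massive transfusion (MT)"). Figure 2 gives ABC only points and a cut-off ("ABC score positive for high risk of massive transfusion if ≥ 2 points"). Section 5.2.4 says BATT predicts a different outcome.

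**Working it through.** **Inputs.** From SAP 5.2.2: Brier B is the mean squared error, 0 at best and 1 at worst; the scaled score is printed as (1 − B)/Bmax; the stated range is 0% to 100%; the stated perfect value is 0%. Assumed, because the documents give neither: Bmax = π(1 − π), which is the Brier score from giving every patient the event proportion π (called non-informative below), and π of 2%, 5%, 10% or 20%.

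**Step 1: direction, with no assumption about Bmax.** Three readings are possible.

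- A, as printed: (1 − B)/Bmax. At B = 0 it equals 1/Bmax, its maximum. It is 0% only at B = 1.
- B, if the fraction is a layout slip: 1 − B/Bmax. At B = 0 it is 100%. It is 0% at B = Bmax.
- C, the form the prose describes: B/Bmax. At B = 0 it is 0%, as stated, but this is not what is printed.

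The SAP's figure, 0% for a perfect score, is reproduced only under C.

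**Step 2: range.** B can reach 1 at any prevalence, when every prediction is certain and wrong. So for any Bmax below 1, A exceeds 100% at B = 0 (it equals 1/Bmax), B falls below 0% at B = 1 (it equals 1 − 1/Bmax), and C exceeds 100% at B = 1. Setting Bmax = 1 restores 0% to 100%, but A and B then both become 1 − B and C becomes B. Nothing is adjusted for baseline risk, and perfect is still 100% under A and B.

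**Step 3: size at π = 5%.** Bmax = 0.05 × 0.95 = 0.0475.

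| Prediction | B | A: (1 − B)/Bmax | B: 1 − B/Bmax | C: B/Bmax |
|---|---|---|---|---|
| Perfect | 0 | 2105% | 100% | 0% |
| 20% better than non-informative | 0.8 × 0.0475 = 0.038 | 0.962/0.0475 = 2025% | 20% | 80% |
| Non-informative | 0.0475 | 2005% | 0% | 100% |
| 20% worse than non-informative | 1.2 × 0.0475 = 0.057 | 0.943/0.0475 = 1985% | −20% | 120% |

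Reading A is at or below 100% only if B ≥ 1 − Bmax, that is 0.9525 at π = 5% and 0.91 at π = 10%.

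**Step 4: does the printed form remove baseline risk?** Algebraically, (1 − B)/Bmax = (1 − B/Bmax) + (1/Bmax − 1). The last term depends on prevalence alone and swamps the first.

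| π | Bmax | A, non-informative | A, perfect |
|---|---|---|---|
| 2% | 0.0196 | 5002% | 5102% |
| 5% | 0.0475 | 2005% | 2105% |
| 10% | 0.09 | 1011% | 1111% |
| 20% | 0.16 | 525% | 625% |

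A non-informative score at 2% (5002%) exceeds a perfect score at 10% (1111%).

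**Step 5: comparing two sets under reading B.** These are illustrative values, not estimates.

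- Set 1: π = 5%, B = 0.038; scaled 1 − 0.038/0.0475 = 20%.
- Set 2: π = 10%, B = 0.6 × 0.09 = 0.054; scaled 1 − 0.054/0.09 = 40%.

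Relative to its own baseline, set 2 is predicted better. Taking 0% as perfect favours set 1, and the unscaled score (0.038 < 0.054) agrees with that wrong reading.

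**The case against.** The strongest reply is that little depends on this. Within one analysed set the unscaled Brier score is also reported, has the right direction, orders scores identically and would expose a reversal. The C-statistic, likelihood ratios and calibration measures are untouched. A value such as 2105% would be noticed at once against a 0% to 100% scale, and the printed fraction may be only a typesetting slip. Section 5.3 makes subgroup work conditional on sample size and does not name the scaled score among the centre-level parameters. All of this stands, and it limits the consequence.

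It does not remove the error. A layout slip leaves the direction reversed, and that form gives plausible values that nobody would query. Step 5 shows that the unscaled score need not expose the reversal between sets with different event rates.

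It can also be said that the range conflict depends on assuming Bmax = π(1 − π). The percentages do; the conflict does not. Step 2 shows that it arises for any Bmax below 1, and Bmax = 1 gives up the section's stated purpose.

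**Conclusion.** The concern holds. The statement that 0% is perfect is wrong for the printed formula and for its likeliest corrected layout, whatever positive value Brier max takes. The stated range fails for any Brier max below 1. The documents do not show which formula was intended.

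The percentages rest on assumed event proportions and on Brier max = π(1 − π); those under reading A also require the fraction to be exactly as printed. The consequence is misreporting or reversed interpretation of one planned performance measure, chiefly where sets with different event rates are compared. Outcomes, data, discrimination and calibration are not affected. It should be fixed before the analysis is run.

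**What to change.** Choose one formula in SAP section 5.2.2 and make the text agree with it.

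- **Preferred:** Scaled Brier = 1 − Brier/Brier max, with Brier max = π(1 − π) and π the observed event proportion in the analysed set, recomputed for each subgroup, centre and outcome. Use a symbol other than p, which the section already uses for the prediction. State that 100% is perfect, that 0% equals giving everyone the observed event proportion, and that negative values are possible. Delete the sentences that call the score a degree of error and make 0% perfect. This form gives 100% for perfect and 0% for non-informative prediction at every prevalence, which is what the section sets out to achieve.
- **If the plain ratio was intended:** print Brier/Brier max with the same definition of Brier max, keep 0% as perfect, and state that 100% is non-informative and that values can exceed 100%.

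The cost is two or three lines of SAP wording. No data and no additional analysis are needed.
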